## 7.4 Study Exit Criteria and Procedures

The reason for study exit will be documented on the appropriate case report forms and in the medical records for each patient who exits the study.

Patients may exit the study for any of the following reasons:

- Screen Failure
- Study Device Attempted But Not Implanted
  - Enrolled patients for whom the implant procedure was prematurely aborted (e.g., entered procedure room and anesthesia induced, but study procedure not attempted (i.e. skin incision to introduce the PASCAL System) or TTVr procedure attempted but did not receive a study device, will be followed for 30 days for safety evaluations only or until resolution of any adverse events related to the implant procedure and then exited from the study.
- Study Device Re-intervention/Explant
  - Patients who have a surgical re-intervention where the device is explanted will be followed for 30 days post-re-intervention for safety evaluations only or until resolution of any adverse events related to the re-intervention and then exited from the study. Patients who have a percutaneous re-intervention where the study device remains in place will continue to be followed for the duration of the study.
- Completion per Protocol
- Withdrawal
  - Patient Withdrawal: The patient may voluntarily withdraw from the clinical study at any time, without penalty or loss of benefits to which they are otherwise entitled.
  - Physician Withdrawal: The Investigator also has the right to withdraw a patient if s/he feels it is in the best interest of the patient to do so.
- Death
- Lost to Follow-up
  - If a patient cannot be reached for a follow-up visit, the Investigator will document the contact efforts made to the patient and/or effort to obtain hospital records in the appropriate electronic case report form. If the patient cannot be reached in any way, or misses a visit, the patient will be considered “unable to contact” for that time interval. After three (3) documented unsuccessful attempts to make contact prove unsuccessful, a certified letter will

be sent to the patient's residence. If there is no response after the certified letter is sent, the patient will be considered "lost to follow-up".

- For patients who are lost to follow-up or withdraw early, Sponsor may request the site to search the Social Security Death Index and/or other death registries and may request the site to obtain the death certificate, if applicable.

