### **12.2.2 As-Treated (Implanted) Population**

The as-treated (implanted) population is a subset of the ITT population and includes all patients in whom the study device is implanted and remains in position at the time of the patient's exit from the procedure room.

The as-treated (implanted) population will be the primary analysis population for performance and additional safety assessment.

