### **12.2.3 Per-protocol (PP) Population**

The per-protocol (PP) population is a subset of as-treated (implanted) population in whom there are no major inclusion/exclusion criteria-related deviations.

Additional analyses of performance and safety data using the PP population will be performed if there is a clinically meaningful difference from the as-treated population.

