6. STATISTICAL ANALYSIS

6.1 General Conventions

- For continuous variables, data will be summarized using the number of observations, mean, median, standard deviation, minimum, maximum, and 95% confidence intervals (based on normal distribution) per table shells. Nonparametric techniques may be used if the data

 Edwards Lifesciences	Revision Date: January 22, 2019		Rev 	For Use Only by Affiliates of Edwards Lifesciences	Page 15 of 25
	Title	Statistical Analysis Plan for Edwards CLASP TR EFS			

does not meet the assumptions of parametric tests.

- For categorical variables, data will be summarized using the number of observations, percentage, and 95% Clopper-Pearson confidence intervals per table shells. In general, the denominator for the percentage calculation will be based on total number of patients with evaluable data for a specified time point unless otherwise specified. Patients with missing data will be excluded from the denominator.
- For time-to-event variables, survival analysis will be used to analyze the data. Summaries will include the number of patients at risk, and number of patients with the event. Patients without events will be censored at their last known event-free time point. If this event-free time point occurs after the analysis time point, the days to event variable will be set equal to the analysis time point so that the patient will be included in the analysis. For patients who did not have an event or early withdrawal and have not yet completed the analysis visit, they will be censored at their last information date. Time to first event curves will be constructed using Kaplan-Meier estimates and all post procedure results will be summarized with Kaplan-Meier estimates of event rates. Hazard ratios, confidence interval for the hazard ratios, and p-values may also be presented from a Cox proportional hazards model.
- For selected variables, in addition to descriptive summary statistics at each follow-up assessment, change from baseline to subsequent time point will be summarized. Paired (i.e., patients with available data at both baseline and respective time point) and unpaired data will be presented separately for selected variables. In general, patients with missing baseline or following-up values will be excluded from the analysis unless otherwise specified.

 Edwards	Revision Date: January 22, 2019		Rev	 For Use Only by Affiliates of Edwards Lifesciences	Page 16 of 25

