6.2 Handling of Missing Data

All statistical analysis on the endpoints will be performed using only those patients with available data required for endpoint analysis. No missing value imputation will be performed unless otherwise specified.

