8.2 Echocardiographic, Clinical and Functional Endpoints

8.2.1 Echocardiographic Endpoints and Parameters

Echocardiographic data will be evaluated by a core laboratory. TTE parameters will be assessed at baseline, discharge, 30 days, 6 months, 1 year and annually until 5 years post procedure. TEE parameters will be assessed at start and end of implant procedure. The change from baseline for selected items will be presented as shift from baseline for each of the pre-specified follow-up periods. Patients that are missing a baseline or follow-up values will be excluded from the analysis.

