8.2.2 Clinical and Functional Endpoints and Parameters

All-cause mortality rates at 30 days, 6 months, 1 year, and annually thereafter and corresponding 95% confidence intervals will be computed using the Kaplan-Meier algorithm with the standard errors being computed using Greenwood's formula.

Heart failure re-hospitalization rates at 30 days, 6 months, 1 year, and annually thereafter will be summarized with counts and percentages.

Re-intervention rates for tricuspid regurgitation at 30 days, 6 months, 1 year and annually thereafter will be summarized with counts and percentages.

Composite of major adverse events (MAE) defined as cardiovascular mortality, MI, stroke, renal complications requiring unplanned dialysis or renal replacement therapy, severe bleeding, unplanned or emergency re-intervention (either percutaneous or surgical) related to the device and major access site and vascular complications requiring intervention at 6 months, 1 year and annually thereafter will be summarized with counts and percentages.

 Edwards	Revision Date: January 22, 2019		Rev	For Use Only by Affiliates of Edwards Lifesciences	Page 23 of 25
	Title		Statistical Analysis Plan for Edwards CLASP TR EFS		

Change from baseline in NYHA Functional Classification and Edema assessment at 30 days, 6 months, 1 year and annually thereafter will be presented as shift from baseline for each of the pre-specified follow-up periods. Patients that are missing a baseline or follow-up values will be excluded from the paired analysis.

Change from baseline in Quality of Life (QoL) score, as measured by Kansas City Cardiomyopathy Questionnaire (KCCQ), Short Form Health Survey (SF-36) and six minute walk test (6MWT) as well as weight, ankle circumference measurement and patient edema questionnaire at 30 days, 6 months and corresponding follow-up visits will be summarized by mean and standard deviation. Patients that are missing a baseline or follow up values will be excluded from the analysis. For the analyses of 6MWT, patients unable to perform the walk due to a medical reason will be considered to have walked an actual distance of zero. eDiary assessments and Activity Monitoring will be summarized using descriptive statistics based on data types and for each pre-specified follow-up periods.

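### Values recorded after a further percutaneous procedure enter the late TR, NYHA and functional summaries unmarked, and may overstate how long the index repair lasts

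*Protocol*

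**What the plan says.** **Follow-up.** Protocol 7.4 treats two kinds of re-intervention differently. For the percutaneous kind: "Patients who have a percutaneous re-intervention where the study device remains in place will continue to be followed for the duration of the study". For the surgical kind: "Patients who have a surgical re-intervention where the device is explanted will be followed for 30 days post-re-intervention for safety evaluations only", or until related adverse events resolve, after which the patient exits. Surgery that leaves the device in place is not mentioned.

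**Populations.** None of them reacts to a later re-intervention. ITT is set at skin incision (Protocol 12.2.1). As-treated requires that "the study device is implanted and remains in position at the time of the patient's exit from the procedure room" (Protocol 12.2.2). Per-protocol keeps as-treated patients "in whom there are no major inclusion/exclusion criteria-related deviations" (Protocol 12.2.3).

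**Late tables.** SAP 8.2.1, on echocardiography: "The change from baseline for selected items will be presented as shift from baseline for each of the pre-specified follow-up periods". SAP 8.2.2, on NYHA and edema: "Patients that are missing a baseline or follow-up values will be excluded from the paired analysis". The general rules are the same: "In general, patients with missing baseline or following-up values will be excluded from the analysis unless otherwise specified" (SAP 6.1) and "All statistical analysis on the endpoints will be performed using only those patients with available data required for endpoint analysis" (SAP 6.2). Under Protocol Tables 9 and 11, TTE, NYHA and edema measures run to 5 years; 6MWT, KCCQ and SF-36 stop at 1 year.

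**Reporting of re-intervention.** It is tabulated separately, but with three scopes. Protocol 12.5 covers unplanned or emergency procedures related to the device. SAP 8.2.2 covers re-intervention for tricuspid regurgitation. Appendix A of the Protocol defines the term as an intervention on the study device already implanted.

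**The concern.** The study is meant to evaluate the performance of the PASCAL System and to guide later designs, with outcomes up to 5 years (Protocol 4). A reader of the 1-year or 5-year TR table will probably take it as the durability of the index repair. Yet a patient whose TR recurs, who has a second percutaneous procedure and then shows mild TR appears in that table as an improved patient, with nothing to mark the difference.

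The plan does treat intervention as failure early on. An intervention before discharge defeats procedural success (device-related only, per SAP 8.1), and a qualifying re-intervention by 30 days defeats clinical success. After that, no rule links re-intervention to the TR or functional results. The SAP does write such rules when it wants them: a patient who cannot walk for a medical reason scores zero on the 6MWT (SAP 8.2.2).

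What is at stake is the durability figure handed to the next trial.

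**Working it through.** The plan states no figure to reproduce. The study is descriptive, and the text after the sample size in Protocol 12.1 is redacted. The check is therefore a sensitivity calculation.

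**Inputs from the documents.** N is up to 65 (Protocol 12.1). The SAP, written to protocol version A, has N = 15 (SAP 2.2).

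**Assumptions, none of them in the documents.** k patients have a percutaneous re-intervention. A share q of them count as responders afterwards. About 70% of the patients without re-intervention respond, which gives R responders (0.7 × (N − k), rounded). Every patient has a value at the visit.

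**Step 1: responder rate.**
- All values: (R + qk)/N
- Re-intervened patients counted as not improved: R/N
- Difference: qk/N, which is at most k/N and is zero when q = 0

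| N | k | R | All values, q = 1 | Counted as not improved | Difference, q = 1 | Difference, q = 0.5 |
|---|---|---|---|---|---|---|
| 65 | 1 | 45 | 46/65 = 70.8% | 45/65 = 69.2% | 1.5 points | 0.8 |
| 65 | 3 | 43 | 46/65 = 70.8% | 43/65 = 66.2% | 4.6 | 2.3 |
| 65 | 5 | 42 | 47/65 = 72.3% | 42/65 = 64.6% | 7.7 | 3.8 |
| 65 | 7 | 41 | 48/65 = 73.8% | 41/65 = 63.1% | 10.8 | 5.4 |
| 15 | 1 | 10 | 11/15 = 73.3% | 10/15 = 66.7% | 6.7 | 3.3 |
| 15 | 2 | 9 | 11/15 = 73.3% | 9/15 = 60.0% | 13.3 | 6.7 |

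Each rescued responder adds 1/65 = 1.5 points at N = 65. If fewer patients have a value at the visit, each one weighs more.

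**Step 2: mean TR grade.** The shift is (k/N) × d, where d is the gain per rescued patient. For k/N of 2% to 15% and d of 1 to 2 grades, it runs from 0.02 × 1 = 0.02 to 0.15 × 2 = 0.30 grade.

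**Step 3: explants.** Suppose s patients exit after surgical explant and so have no later value. The available-data rate is R/(N − s), against R/N if they stay in the denominator as not improved. With s = 5 and R = 42, that is 42/60 = 70.0% against 42/65 = 64.6%, a gap of 5.4 points in the same direction.

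**Step 4: would deleting post-rescue values be enough?** No. Take N = 65, k = 5, R = 42 and q = 0. The all-values rate is already 42/65 = 64.6%. Setting the five aside gives 42/60 = 70.0%, because it removes failed repairs from the denominator.

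**Precision.** The 95% Clopper-Pearson interval for 46/65 is 58.2% to 81.4%.

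**The case against.** Much can be said for the plan as it stands.

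- **Keeping these patients is sound.** Following them and using every observed value answers a legitimate treatment-policy question, and is better than losing them. This stands, and so the all-values tables should stay. But the plan does not say that this is the question its late tables answer.
- **Pooling is inferred from silence.** No sentence says that post-rescue values are results of the index device, and the SAP refers to table shells that are not in the text. This stands as a limit on the wording. The written rules still produce pooling by default, since a missing value is the only stated ground for exclusion.
- **The event is visible.** Re-intervention is an MAE component and a separate endpoint, and SAP 8.2.2 tabulates it over time. This stands in part. Separate counts do not show which patients in the TR table were rescued, and under the Appendix A definition an additional device placed beside the first may not be counted.
- **The shift may be small against the imprecision.** At N = 65 and k = 1 to 7, the not-improved rates of 63.1% to 69.2% all lie inside the interval above. True, but an interval around the all-values rate does not correct a one-sided shift.

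A reader might go further and infer that the bias always favours the device and grows with follow-up. The documents do not support that. The shift is zero when rescue fails, and no re-intervention rate or timing is given.

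**Conclusion.** The gap is real but conditional. By default, values recorded after a percutaneous rescue enter the late summaries unmarked. Where rescue improves the value, those summaries overstate the durability of the index repair by up to k/N: about 1.5 points per rescued responder at N = 65, and nothing when rescue fails. Exit after explant can add to the shift through the denominators. The total depends on k and q, which the documents do not give, so any percentage is an illustration.

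A reader might also infer that the study's performance endpoints are inflated out to 5 years. They are not: device, procedural and clinical success close at the procedure, discharge or 30 days. The exposure is confined to TTE, NYHA and edema measures to 5 years, and 6MWT, KCCQ and SF-36 to 1 year. No hypothesis test is planned for the safety endpoint, and the endpoints are analysed descriptively. This is an inexpensive improvement to how the late tables read, not a flaw that invalidates them.

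**What to change.** Leave Protocol 7.4 follow-up and the all-values tables unchanged. In SAP 8.2.1 and 8.2.2:

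1. **TR grade and NYHA.** Beside each table, add a version in which a patient with any further tricuspid valve intervention after the index procedure (percutaneous or surgical, including explant or an additional device) counts as not improved from that date. The patient stays in the denominator at every later visit, even after exit from the study.
2. **Continuous measures.** Show each summary with and without post-intervention values, and state how many patients are affected. The second version is a companion only; on its own it would drop failed repairs.
3. **No carrying forward.** The last scheduled value may precede the recurrence and so preserve a good grade. Carrying forward would also depart from the SAP's default of no imputation.
4. **One definition.** Use a single definition of re-intervention in Protocol 12.5, Appendix A and SAP 8.2.2, worded so that an additional device is counted.

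**Cost.** One extra table per endpoint, and late figures that may look less favourable. Tabulating re-intervention by visit already calls for event timing, but the sponsor should check that the case report form captures an additional device. The SAP has to be revised in any case, since it is written to protocol version A with 15 patients and the current protocol allows up to 65.

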- In all cases of withdrawal (as described above), withdrawn patients will not undergo further study follow-up procedures after the time of study exit. A study patient who has been withdrawn from the study will not be replaced.
- All data collected up until the time of withdrawal, including imaging studies such as echocardiography scans, will be analyzed in encrypted form and will be kept in encrypted form for the entire duration of the study.

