## 11 ADVERSE EVENT REPORTING AND ASSESSMENTS

Adverse events will be captured for all study patients from the time of enrollment until the patient's participation has ended (i.e. completion of study or withdrawal of consent).

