## 11.2 AE Reporting Requirements

The Investigator will report all adverse events to the Sponsor as soon as possible, but no later than 10 working days after the Investigator first learns of the event.

Each adverse event must be reported on a separate AE CRF. In the event that the EDC system is not in service or otherwise not accessible, the Sponsor must be notified by email [REDACTED]. The AE CRF should be completed as soon as possible thereafter.

At the time of initial notification, the following minimal information must be provided:

- Study site number
- Patient ID number
- Site's awareness date
- AE description
- Causal relationship to device and implant procedure, if known

The site will provide the Sponsor copies of relevant supporting source documentation (e.g. admission H&P, implant procedure report, discharge summary, echocardiogram and laboratory results) for all adverse events requiring CEC adjudication (at a minimum, safety endpoints) and those events determined by the Sponsor to require additional investigation.

Adverse events must be followed until resolution, the patient is lost to follow-up, the patient has withdrawn consent, or the adverse event is otherwise explained.

The Investigator will inform their IRB and FDA of adverse events in accordance with the relevant local and regional regulatory requirements.

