## 11.8 Investigational Device Explants

An Edwards' study device that is explanted at any time with an allegation of device malfunction or deficiency, should be returned to the Sponsor for evaluation. All other explants should be discarded.

Once the study device is explanted, the patient is followed for 30 days after the explant, unless there is an ongoing related adverse event and its outcome is not deemed resolved by the Investigator. Patients will then be exited from the study once AE(s) resolved or 180 days post-explant, whichever comes first. Return kits for explanted devices will be provided upon request by the clinical monitor or study team.

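### Protocol 7.4 ends study follow-up procedures after physician withdrawal even where consent stands, in conflict with 11.2 on open adverse events; 7.4, 11.2 and 11.8 also disagree on when adverse-event follow-up ends after explant

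*Protocol*

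**What the plan says.** **Withdrawal.** Protocol 7.4 lists patient withdrawal and physician withdrawal as separate routes out of the study. On the second it says: "The Investigator also has the right to withdraw a patient if s/he feels it is in the best interest of the patient to do so". No withdrawal of consent is needed. One rule then covers both routes: "In all cases of withdrawal (as described above), withdrawn patients will not undergo further study follow-up procedures after the time of study exit". Data gathered before withdrawal are kept and analyzed. The only later information 7.4 provides for concerns death: "For patients who are lost to follow-up or withdraw early, Sponsor may request the site to search the Social Security Death Index" or other registries, and it may ask for a death certificate.

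**Adverse-event capture and follow-up.** Section 11 captures adverse events from enrollment "until the patient's participation has ended (i.e. completion of study or withdrawal of consent". Section 11.2 sets the rule for events already reported: "Adverse events must be followed until resolution, the patient is lost to follow-up, the patient has withdrawn consent, or the adverse event is otherwise explained". Neither section names physician withdrawal. Section 8.14 ties completion and exit to the requirements of 7.4.

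**Explant.** Where surgical re-intervention removes the device, 7.4 follows the patient for 30 days or until adverse events related to the re-intervention resolve, with no upper limit. Section 11.8 also starts from 30 days and extends this for an ongoing related event, but adds: "Patients will then be exited from the study once AE(s) resolved or 180 days post-explant, whichever comes first".

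**Analysis.** Protocol 12.7 and SAP 6.2 use available data only, and SAP 6.2 imputes nothing unless otherwise specified. SAP 6.1 takes patients with missing data out of percentage denominators. SAP 5.1.3 censors survival analyses at the last information date. SAP 8.2.2 reports heart failure re-hospitalization, re-intervention and MAEs as counts and percentages out to the annual visits.

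**The concern.** A patient withdrawn by the investigator may still carry the implant and may be willing to have information collected. Withdrawal then ends neither device exposure nor consent; it ends data collection. For an adverse event open at that moment, a site cannot follow 7.4 and 11.2 together as written. After explant, a site with an unresolved related event at day 180 faces a similar choice between 11.8 on one side and 7.4 and 11.2 on the other.

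Safety is a stated objective, and Protocol Section 4 promises clinical outcomes up to 5 years. If a patient leaves for a reason connected with prognosis, dropping that patient from the denominator, or censoring as though the exit carried no information, can shift the late rates. Neither document specifies a sensitivity analysis for early exits. The registry search could recover a death, but nothing in 7.4 would recover a non-fatal event.

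**Working it through.** The plan states no figure on this point, so there is none to reproduce. The check compares the texts and then bounds what the analysis rule could do.

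**Step 1: the texts, case by case.**

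| Case | 7.4 | 11.2 | 11.8 |
|---|---|---|---|
| Investigator withdraws patient, consent stands, event open | Study follow-up procedures end | Follow the event | Not applicable |
| Device explanted, related event resolves before day 180 | Exit | Follow-up ends | Exit |
| Device explanted, re-intervention-related event open at day 180 | Continue to resolution | Continue to resolution | Exit |

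The first and third rows conflict; the second does not. In the third row, 7.4 joins 30 days and resolution with a bare *or*. I read it as running to resolution where an event is open. The conflict between 11.2 and 11.8 does not depend on that reading.

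Section 11 is less clear. Its gloss on the end of participation omits physician withdrawal, but a patient who has exited under 7.4 can be regarded as no longer participating.

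**Step 2: which endpoints are exposed.** The 180-day limit runs from the explant, which cannot precede the procedure. It therefore falls after the 30-day MAE time point in every case and can remove only later information. Physician withdrawal can occur at any time, so it mainly affects the 6-month and annual summaries, and would touch the 30-day rate only if it happened before day 30.

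**Step 3: effect of the denominator rule on a late rate.** Inputs: N = 65 (Protocol 12.1, upper limit). Assumed, because the documents give none of them: w = 3 physician withdrawals before 1 year, none with an earlier event, and x = 12 patients with an event among the remaining 62. Let k be the number of withdrawn patients who would later have an event.

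- Reported under the plan: x/(N − w) = 12/62 = 19.4%.
- With full collection: (x + k)/N.

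| k | (12 + k)/65 | Difference from 19.4% |
|---|---|---|
| 0 | 12/65 = 18.5% | −0.9 points |
| 1 | 13/65 = 20.0% | +0.6 points |
| 2 | 14/65 = 21.5% | +2.1 points |
| 3 | 15/65 = 23.1% | +3.7 points |

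The two rates agree when k/w = x/(N − w), that is k = 3 × 12/62 = 0.58. Above that the plan understates the rate; below it the plan overstates it. For scale, the exact 95% interval for 12/62 is 10.4% to 31.4%.

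**Step 4: bound for the 30-day MAE rate, withdrawals before day 30 only.** Assume N = 65, 6 observed events and 3 withdrawals. Available cases: 6/62 = 9.7% (exact 95% interval 3.6% to 19.9%). No withdrawn patient has an event: 6/65 = 9.2%. All three do: 9/65 = 13.8% (6.5% to 24.7%).

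**The case against.** The strongest case on the other side has four parts.

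- **Section 11 can be reconciled with 7.4.** Section 8.14 ties exit to 7.4, so participation, and with it adverse-event capture, can be read as ending at physician withdrawal. This stands. A reader might infer that Section 11 flatly contradicts 7.4; the text does not compel that. What remains is 11.2, for events already open. Calling its silence a gap in a list does not help a site, because the list as written requires follow-up.
- **7.4 does not stop everything.** A reader might infer that all follow-up ends. In fact 7.4 ends study follow-up procedures, keeps earlier data and allows a death-registry search. That search is optional and gives vital status only, so the gap for non-fatal events remains.
- **The harm is inferred.** It is tempting to say that the sickest patients are the ones withdrawn and that harm is therefore understated. The only criterion in 7.4 is the patient's best interest, and neither document gives withdrawal or explant counts or describes who is withdrawn. The illustration depends on assumed counts and can go either way. This stands in full.
- **Nothing decision-bearing changes.** The analyses are descriptive and the safety endpoint has no hypothesis test. Section 11.8 may be meant as an explant-specific outer limit on the general text. Both are fair, and they limit the weight of the point. But the documents do not say that 11.8 overrides 7.4 or 11.2, and estimating safety is what this study is for.

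**Conclusion.** Two conflicts stand in the current protocol. First, 7.4 ends study follow-up procedures after physician withdrawal without withdrawn consent, while 11.2 requires open adverse events to be followed. Second, for a re-intervention-related event open 180 days after explant, 11.8 exits the patient while 7.4 and 11.2 continue.

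The first matters more. Non-fatal events after physician withdrawal go uncollected, and the available-data rule takes the patients out of the late denominators. The late rates may be biased, with size and direction unknown. With 3 withdrawals in 65 and 12 events among the rest, all counts assumed, the possible shift runs from −0.9 to +3.7 points around 19.4%, which is small beside the sampling uncertainty. The second conflict affects late outcomes only.

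This is a worthwhile, inexpensive correction to the protocol. It does not show that safety will be understated, and the 180-day limit does not threaten the 30-day MAE endpoint.

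**What to change.** 1. In 7.4, separate stopping study visits from withdrawing consent for data collection. Suggested sense: physician withdrawal ends clinic assessments only; unless the patient withdraws consent, adverse events, hospitalizations, re-interventions and vital status continue to be collected by telephone or from records at the scheduled times.
2. Align Section 11 and 11.2 with that text, so that physician withdrawal is named and its effect on adverse-event capture is explicit.
3. Reconcile 7.4, 11.2 and 11.8 into one statement of when follow-up of open adverse events ends after explant. The sponsor chooses the duration; this review takes no position on it.
4. In the SAP, say how early exits enter the denominators of the 30-day and later rates.

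Cost: protocol and SAP wording, and a few calls or record checks for what is likely to be a handful of patients. Consent wording may also need a change, but the sample consent form is not visible here and may already cover continued telephone or record follow-up. The change is best made while follow-up is open, since events not collected after exit may be hard to recover later.
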